Short Title	A Microdose Evaluation Study of ABY-029 in Recurrent Glioma
Protocol Number	N/A
Phase	Phase 0 microdose
Methodology	Patients will be administered a single intravenous dose of ABY-029 1-3 hours before surgery. At different times during resection, the coregistered surgical microscope (Zeiss Pentero enabled with intraoperative fluorescence imaging, iFI) will be focused on a point of interest. The surgeon will switch to iFI mode to capture images of the surgical field. Quantitative measurements of fluorophore concentration will be made at the focal point of the operating microscope with an intraoperative probe and biopsy samples will be taken at the coregistered point of interest for subsequent histological analyses and ex-vivo assessments of fluorophore concentration. In addition, an imaging array mounted on second commercial, clinical microscope, will be briefly exchanged with the primary scope to take additional images of the surgical field.
Study Duration	12-18 months
Study Center(s)	Single-center, Dartmouth-Hitchcock Medical Center
Objectives	The primary study objective is to determine if microdoses of ABY-029 (up to 6X) lead to detectable signals (defined as signal-to-noise ratio, SNR ≥ 10 , with wide-field iFI) in sampled tissues with an EGFR pathology score ≥ 1 based on histological staining. The secondary study objective is to assess diagnostic accuracy of ABY-029 detection by iFI and intraoperative probe relative to histopathology diagnosis, and other indicators (e.g. proliferation, infiltration, etc.) as the gold standard, and to measure the molecular uptake and concentration of ABY-029 in resected specimens.
Number of Subjects	A minimum of 6 and a maximum of 12 adult patients with a diagnosis of recurrent glioma will be enrolled.
Diagnosis and Main Inclusion Criteria	Operable brain tumor in adults with pre-surgical diagnosis of recurrent glioma.

Study Product, Dose, Route, Regimen	
Criteria for successful iFI are locations of all EGFR positive samples (defined as having a pathology score ≥ 1 based on histological staining) having a measurable signal (defined as SNR ≥ 10). A single microdose of ABY-029 at 30 nanomoles (237μg) will be injected into the first 3 patients. If samples from these subjects meet successful iFI criteria, 3 more patients will be enrolled at the same dose, concluding the study with a total of 6 subjects. Otherwise, the ABY-029 dose in the next 3 patients will be increased to 3X (90 nanomoles, 711 μg). If samples from these subjects meet successful iFI criteria, 3 more patients will be enrolled at the 3X dose, concluding the study with a total of 9 subjects. If iFI criteria are not met, the next 3 patients will be enrolled at 6X dose (180 nanomoles, 1.42 mg). If iFI criteria are met, 3 more patients will be enrolled the 6X dose, concluding the study with a total of 12 subjects. If iFI criteria are not met in the first 3 patients at the 6X dose, enrollment will be stopped with a total of 9 subjects.
 
Because of the microdosing levels used, the results of the Dartmouth Toxicity Study (at 10X, 100X, 1000X doses), and the safety profile of similar compounds (e.g. ABY-025), we do not anticipate any serious adverse events (SAEs) related to ABY-029.

Duration of administration	ABY-029 will be administered by IV injection on day of surgery, approximately 1-3 hours prior to the procedure.
Reference methods	Post-operative histopathology will serve as the gold standard.
Statistical Considerations	Repeated measures analyses of variance will be performed to account for multiple samples from each patient. Student's t-test will be used to evaluate ABY-029 fluorescence signal detection in tumor relative to normal brain with iFI and intraoperative probe. Empirical ROC curves and logistic regression analysis for clustered binary data will be used to evaluate the accuracy of ABY-029-specific fluorescence in discriminating between EGFR+ glioma tumor, EGFR- glioma tissue, and normal tissue when detected by iFI and/or intraoperative probe.

1 Introduction

This document is a clinical research protocol and describes a human research study. This study will be conducted according to US and international standards of Good Clinical Practice (FDA Title 21 part 312 and International Conference on Harmonization guidelines), applicable government regulations and Institutional research policies and procedures. All personnel involved in the conduct of this study have completed human subject protection training.

1.1 *Background Information*

The focus of this exploratory investigational new drug (eIND) development is to realize a fluorescent reporter to guide neurosurgical glioma resection using a synthetic peptide that binds to the epidermal growth factor receptor (EGFR) and provides an optical fluorescent signal of the concentration. The combined peptide and fluorophore will be called ABY-029, and is the focus of this first-in-human trial in neurosurgery. The initial focus of this Phase 0 clinical study is evaluation of drug uptake and concomitant imaging signal.

This research is funded by NIH under grant R01 CA167413. Following completion of the manufacturing and nonclinical plans, we will submit an exploratory IND (eIND) to FDA. Depending on the findings from clinical studies conducted under eIND, we anticipate the submission of a traditional IND.

Several groups have pioneered the use of fluorescence imaging in experimental surgery [1] and a platform of targeted compounds for surgical applications [2-5] in which the surgeon's white light visual field is augmented with fluorescent-guided information. Perhaps the largest clinical experience with fluorescence-guided resection has been gained in neurosurgery with aminolevulinic acid (ALA) induced protoporphyrin IX (PpIX). The approach has been evaluated in a prospective randomized Phase III trial [6] with sufficiently positive outcomes to alter standard-of-care in Germany for surgical resection of high grade glioma [7] and related studies have been completed and are ongoing at Dartmouth under FDA IND #77,751 for oral administration of ALA [8-12].

Clinical motivation exists for pursuing new brain tumor fluorescent probes beyond PpIX for guiding surgical resection. First, ALA-induced PpIX fluorescence is enhanced by non-tumor-specific molecular processes related to increased metabolism and blood-brain-barrier breakdown. Second, while these processes provide reliable enhancement in high-grade glioma tumors, enhancement at the margin and in low-grade glioma is relatively poor. Third, the anti-EGFR ABY-029 molecule we are developing has potential to guide a range of oncologic surgeries, given the large number of tumor types overexpressing EGFR. Most importantly, a wealth of information exists on EGFR fluorophore targeting [13-25] [26-28] which suggests our approach is likely to be successful and could benefit patients with malignant glioma and other cancers whose prognosis is improved by complete surgical resection.

1.2 *Investigational Agent*

The production of the investigational drug to be used in the clinical study, ABY-029, is being coordinated by Dartmouth with project partners Affibody AB, LI-COR Biosciences, and the University of Alabama at Birmingham (UAB) Vector Production Facility, with Bachem AG (Switzerland) as the manufacturing subcontractor.

The Swedish biotechnology company Affibody AB has developed a group of molecules which are small, single domain, non-immunoglobulin proteins based on a 58 amino acid, three-alpha-helical scaffold [29, 30]. The target binding site is composed of 13 surface-exposed amino acids on helix 1 and helix 2. By randomizing these 13 amino acids, the company has created large libraries of Affibody® molecules from which ones that bind to a given target protein are selected (examples include EGFR, HER2 or PDGFR β [31-33]). Their small size and stability, high affinity and target recognition specificity, and rapid biodistribution kinetics and clearance make them ideal for in vivo targeting. Affibody molecules can be produced either by recombinant techniques in bacteria or by conventional peptide synthesis and can be modified with functional groups for fluorescent or radioactive labels. Site specific modification of Affibody molecules is achieved by introducing a single cysteine which can be used for modification of maleimide-activated functional groups leading to defined and homogenous products [34].

LI-COR is a privately held company that is committed to the development of in vivo fluorescence imaging during surgery and has been systematically developing near-infrared (NIR) fluorescent molecules with the goal of creating in vivo reporters for targeted contrast. IRDye 800CW is a NIR dye that can be functionalized with either an NHS or maleimide reactive group, allowing it to be attached to a number of biomolecules.[35] Recently, cetuximab conjugated to IRDye 800CW was used at the University of Alabama in a dose escalation study in 12 patients with squamous cell carcinoma in the head and neck. After passing through FDA safety and pharmacokinetic studies, the investigators showed positive correlation between fluorescence markers and EGFR levels, and demonstrated that fluorescently labelled molecules can be safely administered to humans to identify tumor cells with sub-millimeter resolution [36].

The ABY-029 conjugate is produced by first incubating the Z03115-Cys peptide with Dithiothreitol (DTT), to break up Affibody dimers that naturally form, and then mixing the peptide with IRDye 800 CW maleimide dye, at a ratio of one dye molecule per peptide molecule.

Z03115-Cys is a synthetically generated 59 amino acid peptide produced by Bachem (Switzerland). The peptide has a molecular formula of $C_{299}H_{468}N_{78}O_{92}S_3$ and is composed of (H-Ala-Glu-Ala-Lys-Tyr-Ala-Lys-Glu-Met-Trp-Lle-Ala-Trp-Glu-Glu-Lle-Arg-Asn-Leu-Pro-Asn-Leu-Asn-Gly-Trp-Gln-Met-Thr-Ala-Phe-Lle-Ala-Lys-Leu-Leu-Asp-Asp-Pro-Ser-Gln-Ser-Ser-Glu-Leu-Leu-Ser-Glu-Ala-Lys-Lys-Leu-Asn-Asp-Ser-Gln-Ala-Pro-Lys-Cys-OH).

The dye is coupled to the peptide molecule via maleimide chemistry at a single Cys residue at the C-terminus of the peptide, as illustrated schematically below. The conjugation reaction is followed by purification from free dye.

[figure not shown]

Figure 1 - Schematic view of ABY-029 (Z03115-Cys-Mal-IRDye800CW)

The solid phase peptide synthesis production of Z03115-Cys has been subcontracted to Bachem AG (Bubendorf, Switzerland). Bachem has automated systems for generation of pharmaceutical grade product, and a long history of production for human use. The maleimide linkage conjugation of Z03115-Cys with IRDye800CW has been subcontracted to the University of Alabama at Birmingham Vector Production Facility, and will be conducted in their cGMP laboratories.

Physical Form:	Clear, green-blue liquid.
Molecular Formula:	Cys-((RS)-1-[2-maleimido-ethyl]-IRDye 800CW-OH)
Molecular Weight:	7914.95 grams/mole
Solubility:	Soluble in Phosphate Buffered Saline (PBS)
pKa Value:	6.84E+05
pH Value:	7.4

Kd Value: 1 nanomolar (nM)

The drug will be supplied in vials containing 5 mL of liquid Phosphate Buffered Saline (PBS).

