1.5 Dose Rationale

We plan a sample size of 6-12 patients in this open label, single center, clinical trial of ABY-029. Administration will occur as a single intravenous injection to subjects with recurrent glioma, approximately 1-3 hours prior to surgery. The protocol is not a safety study since no physiological effects are expected at microdose levels of ABY-029. Rather, doses have been selected to determine if a fluorescence signal can be detected by wide-field imaging technology with a signal-to-noise ratio of 10, which is considered necessary for subsequent assessment of diagnostic performance of ABY-029 as a tumor biomarker sufficient to guide surgical resection in the future. No diagnostic or therapeutic intent is proposed, and administration of the study drug is not intended to alter the extent of planned brain tumor resection during the surgical procedure.

Dosing Scheme: A single microdose of ABY-029 at 30 nanomoles (237 μ g) will be injected into the first 3 patients. If samples from these subjects meet successful iFI criteria (defined as SNR \geq 10 at locations of samples with EGFR pathology score \geq 1 based on histological staining), 3 more patients will be enrolled at the same dose, concluding the study with a total of 6 subjects. Otherwise, the ABY-029 dose in the next 3 patients will be increased to 3X (90 nanomoles, 711 μ g). If samples from these subjects meet successful iFI criteria, 3 more patients will be enrolled at the 3X dose, concluding the study with a total of 9 subjects. If iFI criteria are not met, the next 3 patients will be enrolled at 6X dose (180 nanomoles, 1.42 mg). If iFI criteria are met, 3 more patients will be enrolled at the 6X dose, concluding the study with a total of 12 subjects. If iFI criteria are not met in the first 3 patients at the 6X dose, enrollment will be stopped with a total of 9 subjects.

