4.1 Patient Selection

Patients with recurrence of presumed high grade glioma having EGFR positive tissue (score ≥ 1 based on histological staining or molecular pathology analysis) obtained from prior surgery will be eligible to participate.

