5.1 Description

Patients will be administered ABY-029 by intravenous injection approximately 1-3 hours prior to induction of anesthesia. The range of approximately 1-3 hours is acceptable given pre-clinical data indicating that imaging signal levels appear to be stable over this time period. Time from ABY-029 administration to surgery is collected. Subjects are considered enrolled in the study once ABY-029 has been injected.

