6.1 Surgical Visit

After the study drug is administered (~1-3 hours prior to surgery), the patient will be prepared and transported to surgery as per routine at Dartmouth-Hitchcock. In the OR, patient positioning, registration of the MR image-guidance system, preparation of the surgical field, and draping will follow standard practice, as will scalp incision and craniotomy. Upon opening of the dura, the coregistered and tracked Zeiss Pentero operating microscope adapted for intraoperative fluorescence imaging (iFI) at 800 nm will be brought in to begin conventional image-guided microsurgical technique for tumor resection. At approximately 4 time points during each surgery and/or at the discretion of the surgeon, data/image and specimen acquisitions will occur. Three (3) will typically occur at first exposure of tumor, at the approximate mid-point of tumor resection (when a significant tumor tissue is in the field), and at a point nearing but prior to completion of tumor resection (when small amount of tumor tissue remains), and a fourth may occur at presumed end of resection. At each time point, iFI acquisitions will be recorded. The surgeon will then focus the coregistered microscope at discrete points in the operative field which exhibit non-, weakly, moderately, and strongly fluorescent emissions, if evident on the iFI scan. At each point, a second iFI will be acquired, optical probe measurements will be recorded and a surgical biopsy specimen will be obtained (except at presumed end of resection when no more tissue is planned for excision). Since the 2nd iFI, probe data and biopsy sample will occur each time at the focal point of surgical microscope which is coregistered, all intraoperative images, data and specimens will also be coregistered. If no signal is evident on the iFI scan, the surgeon will sample several locations in the surgical field by focusing the operating microscope on points of interest intended for resection, performing the probe measurements and biopsying the positions for later analysis. iFI and optical probe readings will also be acquired from normal brain to establish baseline/background signal levels for the case. Additionally, an imaging module mounted on a second commercial, clinical microscope, will be used to acquire images during surgery. Acquiring these images will involve moving the primary clinical scope out of the field, positioning the new scope to acquire images, and moving the primary scope back into place. This process will take approximately three minutes or less and poses no additional risk to the patient. When the case is performed in the Center for Surgical Innovation, and when indicated clinically, iMR (intraoperative MRI) may be acquired and resection may continue based on the findings. In these cases, iFI, optical probe and biopsy may occur at locations planned for resection. We have used these same coregistered image, data, and biopsy procedures in our current studies of ALA-induced PpIX fluorescence and have collected high quality information from up to 12-16 surgical specimens per case (~10 on average).

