6.3 Specimen Analysis

Biopsy samples taken at the time of surgery for research purposes and processed for IHC will be scored by a pathologist according to the following criteria: 0 = no staining; 1 = low membranous staining around cells; 2 = medium membranous staining completely around cells; and 3 = high membranous staining completely around cells. Standard formalin-fixation with paraffin embedding will be used for histopathologic type and grade to confirm diagnosis of astrocytoma or glioblastoma (following WHO criteria) by the study neuropathologist. As these tumors are recurrences and patients have received radiation and chemotherapy, an assessment of reactive gliosis vs. residual/recurrent glioma will also be scored as well as tumor burden and necrosis using methods previously described. Here, histopathology will be classified as non-tumor tissue, solid tumor, infiltrating tumor, or indeterminate. Infiltrating tumor will be further graded into <33% tumor, >33% but <67% tumor, and >67% tumor). Proliferation will be assessed by quantitatively scoring Ki-67 immunopositive cells. ABY-029 binding to tumor cells in the specimen will be evaluated by performing IHC with secondary antibodies directed against the anti-EGFR Affibody following the protocol. EGFR protein expression often corresponds to gene amplification, thus, we will assess gene-protein correlations on a cell-by-cell basis by performing both IHC for EGFR protein and CISH for EGFR gene amplifications using a multi-spectral analysis microscope (Nuance) to distinguish in individual tumor cells. Frozen tissue will be solubilized and evaluated for quantitative fluorescence using fluorimetry. Western and/or ELISA will be used if the signal is not sufficiently strong.

7 Statistical Plan

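### The imaging criterion requires SNR ≥ 10 in every EGFR-positive specimen but fixes no number of such specimens, so the verdict depends strongly on the specimen count as well as on the agent

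*Combined protocol and SAP*

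**What the plan says.** The Study Summary (Study Product, Dose, Route, Regimen) defines success at the level of the specimen: "Criteria for successful iFI are locations of all EGFR positive samples", with positive meaning a pathology score of at least 1, having SNR ≥ 10. The specimens of the first three patients at a level are judged together: "If samples from these subjects meet successful iFI criteria, 3 more patients will be enrolled at the same dose". If the criterion is not met, the study moves to the next level, or stops after the last one. Section 1.5 gives the same threshold but applies it "at locations of samples with EGFR pathology score" ≥ 1, without *all*.

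Section 6.1 has the surgeon focus on "discrete points in the operative field which exhibit non-, weakly, moderately, and strongly fluorescent emissions, if evident on the iFI scan" and take a biopsy at each point, except at presumed end of resection. If nothing fluoresces, several locations are sampled anyway.

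On numbers, section 7.1 estimates at least 6 specimens per case, more typically 12 to 16, and assumes an average of 10. Section 7.2 carries this to 30 per three-patient group. These are counts of all specimens, whatever their EGFR score. The positive tissue needed for eligibility is that "obtained from prior surgery will be eligible to participate" (section 4.1), not the tissue sampled in this study. Section 5.1 states: "Subjects are considered enrolled in the study once ABY-029 has been injected". Section 4.5.1 allows data to be left out of the final analysis for dose, timing or diagnosis, but no section provides for replacement.

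**The concern.** A criterion that tolerates no miss has a pass probability that falls as the number of EGFR-positive specimens rises. The protocol leaves that number open. It depends on how many points are sampled in each operation and how many later score 1 or more. Two groups of three patients given an equally detectable agent can therefore face very different chances of passing.

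The open denominator also matters at the low end. A patient whose specimens all score 0 uses one of the three places and meets the criterion by default; if that happened in all three, the criterion would be met with no evidence. Since the verdict steers the study and bears on the primary objective, its behaviour should be known in advance. Section 7.1 sizes only differences in mean signal and gives no pass probability for this criterion.

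**Working it through.** **The plan's own figures.** Section 7.1 states detectable differences at 80% power and two-sided 0.05. A one-sample (paired) t-test with patients as units gives 3.26 SD for 3 patients (stated 3.3) and 1.43 SD for 6 (stated 1.4). So the samples-versus-normal-brain figures reproduce, but they concern means and say nothing about the chance of meeting the criterion.

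**Inputs from the documents.** Three patients per verdict; about 10 specimens per case and 30 per group (7.1, 7.2); no miss allowed (Study Summary).

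**Assumptions, because the documents give no values.** p is the chance that one EGFR-positive specimen reaches SNR 10. n is the number of EGFR-positive specimens in the three patients, split equally. ρ is the ICC within a patient. Taking n = 30 means that every projected specimen is positive, which is the upper end at the average of 10 per case.

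**Independent specimens.** P(met) = p^n. At p = 0.95: 0.95^3 = 0.857 and 0.95^30 = 0.215.

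**Clustered specimens.** Let each patient's detection rate follow a Beta(a, b) distribution with a = p(1−ρ)/ρ and b = (1−p)(1−ρ)/ρ. For k specimens in one patient, P(all detected) is the product of (a+i)/(a+b+i) over i = 0 to k−1. The three-patient result is its cube. At p = 0.95 and k = 10:

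- ρ = 0.1: a = 8.55, b = 0.45; per patient 0.700; cubed 0.343.
- ρ = 0.3: a = 2.217, b = 0.117; per patient 0.803; cubed 0.518.

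**Probability that the criterion is met**

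| p | ρ | n = 3 | n = 6 | n = 15 | n = 30 |
|---|---|---|---|---|---|
| 0.80 | 0 | 51% | 26% | 3.5% | 0.1% |
| 0.80 | 0.3 | 51% | 33% | 14% | 6% |
| 0.90 | 0 | 73% | 53% | 21% | 4% |
| 0.90 | 0.3 | 73% | 59% | 39% | 26% |
| 0.95 | 0 | 86% | 74% | 46% | 21% |
| 0.95 | 0.1 | 86% | 75% | 53% | 34% |
| 0.95 | 0.3 | 86% | 77% | 63% | 52% |
| 0.98 | 0 | 94% | 89% | 74% | 55% |
| 0.98 | 0.3 | 94% | 90% | 83% | 77% |

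At n = 3 there is one specimen per patient, so ρ has no effect.

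**Two readings of the table.** Down a column, the agent matters: at n = 15 and ρ = 0, going from p = 0.80 to 0.98 raises the chance from 3.5% to 74%. Along a row, the count matters: at p = 0.95 it falls from 86% to 21% (ρ = 0) or 52% (ρ = 0.3). The order of two agents can reverse: p = 0.90 on 3 specimens (73%) passes more often than p = 0.95 on 30, even at ρ = 0.3 (52%).

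**What a pass shows.** Under independence, the one-sided 95% lower bound for p after n of n detected is 0.05^(1/n): 0.37 for 3 of 3 and 0.90 for 30 of 30. With n = 0 the criterion is met without any information.

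**Across all three levels.** For illustration, suppose detection is 90%, 95% and 97% at the successive levels with 20 EGFR-positive specimens each (7, 7 and 6 per patient). The chance that the criterion is never met is then (1−0.122)(1−0.358)(1−0.544) = 26% under independence, (1−0.196)(1−0.451)(1−0.622) = 17% at ρ = 0.1, and (1−0.333)(1−0.582)(1−0.724) = 8% at ρ = 0.3.

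**The case against.** In the plan's favour, a strict gate is open to a Phase 0 study that regards SNR 10 as necessary for later diagnostic work. The endpoint in 3.2 is SNR by EGFR score, and 7.2 analyses it by t-test, ANOVA and correlation whether or not the gate is passed. Very small denominators are unlikely with 6 or more specimens per case in patients selected for EGFR-positive tumour. Specimens cluster within patients, as the plan itself recognises, so independence gives the extreme figures. These points stand. They reduce the size of the effect but do not supply a minimum count, a rule for a patient with no positive specimen, or a pass probability.

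Three stronger readings are tempting, and the documents do not support them.

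- *The verdict depends on sampling more than on the agent.* No detection rate or EGFR-positive fraction is given. Under independence the two effects are of similar size over the ranges shown, and at ρ = 0.3 the agent's effect is the larger.
- *Section 6.1 directs the surgeon to specimens that break the rule.* A non-fluorescent point counts against the criterion only if it later scores 1 or more and its SNR is below 10. That is a genuine miss in EGFR-positive tissue, which is what the primary objective asks about. Section 6.1 also says such points are chosen only if evident, and does not define weakly fluorescent as SNR below 10. The accuracy analyses need these points.
- *The protocol expects reactive gliosis instead of tumour in some patients.* Section 6.3 says only that "an assessment of reactive gliosis vs. residual/recurrent glioma will also be scored". It does not predict how often gliosis will be found.

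**Conclusion.** The concern holds in this form: the criterion allows no miss, its denominator is not fixed, a patient with no EGFR-positive specimen satisfies it by default, and its two statements differ on *all*. The verdict therefore depends strongly on how many EGFR-positive specimens are taken as well as on the agent. At 95% detection the chance of meeting it is 86% with 3 specimens, and 21%, 34% or 52% with 30 at ICC 0, 0.1 or 0.3. These sizes rest on assumed detection rates, counts and ICCs. The direction does not: with any detection rate below 100% and imperfect correlation, more specimens mean a lower chance of passing. The sponsor should act on this, but it does not invalidate the planned signal analyses.

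**What to change.** 1. Reconcile the Study Summary and section 1.5 on whether every EGFR-positive specimen must reach SNR 10.
2. State that a patient counts toward the three-patient imaging verdict only if at least one specimen with an iFI reading scores EGFR ≥ 1. Otherwise the verdict waits for the next patient at that level, taken from the expansion places so that the stated maximum of 12 holds. Three levels of three use 9 places, so at most 12 − 9 = 3 such patients can be absorbed if all levels are used. The text should say what happens beyond that, and the stated totals of 6, 9 and 12 need matching wording.
3. In 7.2, report for each dose the proportion of EGFR ≥ 1 specimens with SNR ≥ 10, averaged over patients, with an interval that allows for clustering and the number of EGFR-positive specimens per patient. Base the primary conclusion on this proportion rather than on the all-or-none result alone. The per-patient counts matter because a patient with one positive specimen carries a third of the weight in a group of three.
4. Tabulate the pass probability of whichever criterion is kept over a range of specimen counts and ICCs.

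The dose steps and any threshold stay with the sponsor. The cost is protocol wording, an occasional extra patient at a level, fewer expansion places, and a slightly less absolute claim of success. Item 2 removes the default pass but still lets a group pass on 3 specimens, so item 3 is needed as well.

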4.2 Inclusion Criteria

The following criteria must be met by study subjects to be eligible for study enrollment:

- 1) Preoperative diagnosis of recurrent high-grade glioma having EGFR positive tissue from prior surgery.

- 2) Tumor judged to be suitable for open cranial resection based on preoperative imaging studies.
- 3) Valid informed consent by subject.
- 4) Age \geq 18 years old.

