4.5 Early Withdrawal of Subjects

4.5.1 When and How to Withdraw Subjects

Subjects participate in a "one-time" event (i.e., surgery) as part of this study and are not expected to be withdrawn because of subsequent post-surgical conditions and/or scenarios (e.g. the need for alternative and/or additional treatment). Subjects may withdraw their consent at any time prior to surgery. Subject data collected per protocol may subsequently not be included in the final analysis, if IV administration of ABY-029 is found not to have occurred at the proper dose (237 μ g, 711 μ g or 1.42mg, depending on the dose group) approximately 1-3 hours prior to surgery or the definitive post-operative diagnosis does not meet the presumed entry criteria.

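### The reference-standard result can decide whether a patient enters the accuracy analysis: section 4.5.1 permits exclusion on post-operative diagnosis and makes no exception for the secondary objective

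*Combined protocol and SAP*

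**What the plan says.** The Study Summary names the reference method: "Post-operative histopathology will serve as the gold standard". Section 7.2 analyses accuracy per biopsy. Tumor status is the binary outcome of a logistic mixed model with a random effect for each subject, summarised by a concordance index built from the fitted probabilities. The Study Summary also promises empirical ROC curves.

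Section 4.5.1 contains the exclusion: "Subject data collected per protocol may subsequently not be included in the final analysis" if, among other triggers, "the definitive post-operative diagnosis does not meet the presumed entry criteria". The entry criterion in 4.2 is "Preoperative diagnosis of recurrent high-grade glioma having EGFR positive tissue from prior surgery".

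Section 6.3 gives the study neuropathologist two tasks. One is "histopathologic type and grade to confirm diagnosis of astrocytoma or glioblastoma"; the other is to supply the specimen classes: "histopathology will be classified as non-tumor tissue, solid tumor, infiltrating tumor, or indeterminate". Because these patients have already had radiation and chemotherapy, "an assessment of reactive gliosis vs. residual/recurrent glioma will also be scored as well as tumor burden and necrosis".

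Section 7.3, on analysis populations, restates eligibility. It defines no separate set for accuracy and does not say that patients with an unconfirmed diagnosis are kept.

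**The concern.** An accuracy study should choose its patients by what was known before the index test and the reference test. Here the reference test can remove a patient afterwards.

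The foreseeable case is a presumed recurrence that turns out to be treatment effect only. Such a patient fails the entry criterion and contributes only non-tumor biopsies. If the agent accumulates in treated, tumor-free tissue, those biopsies are where it would give false positives. The preclinical sections make this plausible without establishing it for humans. Section 1.3.2 attributes low uptake in normal rat brain to the blood-brain barrier, and the work in 1.3.1 used a reference tracer to separate vessel leakage from binding.

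At stake is whether the reported ROC area describes everyone operated on for a presumed recurrence or only those whose recurrence was confirmed. The plan does not say which it intends.

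**Working it through.** **Plan's own figures.** The documents give no sensitivity, specificity, ROC area, proportion of non-tumor biopsies or rate of unconfirmed diagnosis. The detectable differences in 7.1 concern mean signal and do not bear on this point. Everything below other than patients per dose and specimens per patient is an assumption.

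**Step 1: does the rule reach the accuracy analysis?** 4.5.1 refers to the final analysis without limiting it to the primary objective, and 7.2 and 7.3 give no exemption. The trigger (post-operative diagnosis) and the reference classes both rest on the histopathology described in 6.3. So the rule does reach it, at someone's discretion.

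**Step 2: how much non-tumor material could one patient hold?** Section 7.2 gives 3 to 6 patients per dose and 10 specimens per patient on average. Assume one unconfirmed patient with all 10 biopsies non-tumor, and a fraction f of non-tumor biopsies in the other n − 1 patients:

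share removed = 10 / [10 + 10 f (n − 1)]

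| n | f = 0.1 | f = 0.4 |
|---|---|---|
| 3 | 10/12 = 83% | 10/18 = 56% |
| 6 | 10/15 = 67% | 10/30 = 33% |

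The specimens left number 2 to 8 (n = 3) or 5 to 20 (n = 6).

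**Step 3: effect on the empirical AUC.** Assume 12 patients (which happens only if all three doses are used and pooled), 10 specimens each, and 8 tumor and 2 non-tumor specimens per confirmed patient. Let k patients have treatment effect only. Signals are normal with SD 1: tumor mean 2.2, non-tumor in confirmed patients 0, treatment-effect patients s. For two such distributions d apart, AUC = Φ(d/√2).

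- Tumor against ordinary non-tumor: Φ(2.2/√2) = 0.940. This is the value reported after exclusion.
- Tumor against treatment effect, s = 0.5: Φ(1.7/√2) = 0.885.
- Tumor against treatment effect, s = 1.5: Φ(0.7/√2) = 0.690.

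With everyone kept, AUC = [2(12 − k) × 0.940 + 10k × Φ((2.2 − s)/√2)] / [2(12 − k) + 10k].

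| k | Non-tumor specimens dropped | AUC kept, s = 0.5 | AUC kept, s = 1.5 |
|---|---|---|---|
| 1 | 10 of 32 (31%) | 0.923 | 0.862 |
| 2 | 20 of 40 (50%) | 0.913 | 0.815 |
| 3 | 30 of 48 (63%) | 0.906 | 0.784 |

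At s = 0 the value stays at 0.940 and only precision is lost. At s = −0.5, Φ(2.7/√2) = 0.972, and the kept AUC is (22 × 0.940 + 10 × 0.972)/32 = 0.950 for k = 1 and (18 × 0.940 + 30 × 0.972)/48 = 0.960 for k = 3. Exclusion would then understate accuracy.

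**Step 4: effect on the planned model-based index.** Section 7.2 does not say whether the fitted probabilities include the estimated subject effect. I simulated the Step 3 scenario and fitted a random-intercept logistic model, with 100 runs for each k at s = 0.5 and s = 1.5. With the subject effect in the predictions, the index was about 0.94 to 0.95 with exclusion and rose to 0.96 to 0.98 with everyone kept: the model learns which patients have no tumor. With the subject effect left out, it followed Step 3 (0.94 to 0.95 with exclusion, 0.92 to 0.78 with everyone kept).

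**The case against.** A reader might infer that the specimens testing specificity are lost altogether. They are not. The unit is the biopsy, 6.3 has a non-tumor class, and 6.1 has the surgeon sample non-fluorescent as well as fluorescent points. Reactive gliosis can also be found alongside tumor, so confirmed patients may supply treatment-effect specimens too. Step 3 puts all the raised signal in the dropped patients, and its bias follows from that choice.

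A reader might also infer that accuracy will be overstated. The documents do not support that as a certainty. Exclusion is permitted rather than required, uptake in treated human tissue is unknown, and an unconfirmed diagnosis may be another tumor type or grade. Removing such a patient could affect sensitivity as well. For the model-based index, the direction reverses if predictions carry the subject effect.

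There is also a case for the restriction itself. The Study Summary frames the comparison as EGFR-positive glioma, EGFR-negative glioma and normal tissue, so confirmed glioma is an arguable target for a Phase 0 study. The objective is secondary, and the dose steps depend on the signal-to-noise criterion, not on an ROC area.

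All of this limits the size and certainty of the point. None of it supplies the missing exemption or says that a confirmed-only population was intended. Substitution from confirmed patients may also be thin: under 6.1, biopsies come from tissue to be resected, and no biopsy is described for the normal-brain readings.

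**Conclusion.** The concern holds as a risk of selection on the reference standard. Under 4.5.1 the histopathology that judges the agent may also decide whether a patient is counted, and nothing in 7.2 or 7.3 prevents this for the accuracy objective.

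On the Step 2 assumptions, one treatment-effect-only patient could hold 33% to 83% of the non-tumor specimens at a dose. On the Step 3 assumptions, the empirical AUC would be 0.94 with exclusion against 0.92 to 0.78 without it. Those figures rest on an assumed number of unconfirmed patients, an assumed 80/20 specimen split, a 2.2 SD separation, a shift of 0.5 to 1.5 SD confined to the dropped patients, and one signal distribution across pooled doses. They illustrate what could happen and do not predict this trial's result. The change is worth making because it is cheap and removes the dependence whichever way the bias runs.

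**What to change.** In 4.5.1, state that exclusion on post-operative diagnosis does not apply to the secondary accuracy analysis.

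In 7.2, state that this analysis includes every injected patient with coregistered imaging and biopsies, whatever the final diagnosis, and that results restricted to confirmed recurrent high-grade glioma are reported as a sensitivity analysis.

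Also in 7.2, base the ROC area or concordance index on the empirical signal or on fitted probabilities without the subject-specific random effect. Without this third change, keeping patients who have no tumor specimens could inflate the index, as Step 4 shows.

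The cost is a few sentences and one extra analysis, with no new data and no change to patient care. The downside is that the reported accuracy may be lower.
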